1. **Global Rating of Change score:** To assess overall change from initial presentation, the GROC will be recorded at each follow up visit. This score is rated from -7 to +7 where subjects will select an answer that best describes their current perceived status since injury onset.^{23,45}
2. **PSFS:** The PSFS is a self-report questionnaire assessing pain, instability and activities of daily living (ADLs).⁶
3. **SPADI:** The SPADI is a self-report questionnaire assessing pain and

648 disability.^{48,49}

649 4.

650

651 6.4.2 Data analysis

652

653 Descriptive statistics will be provided. Data analysis will be performed with statistical
654 analysis software R version 3.1.2. A 2x4 repeated measures ANOVA with Sidak's post hoc
655 testing will be used with time as the within-subjects factor and group (control or TDN) as the
656 between-subjects factor. Alpha will be = .05.

657

658 6.4.3 Safety Monitoring and Analysis Plan.

659 For this study, continuous assessment of participant's response to treatment will be
660 performed, especially their response to dry needling techniques. If the participant experiences
661 soreness greater than expected or has hematoma develop increasing in size then needling
662 techniques will be discontinued. At any time the subject can elect to discontinue participation
663 in the study and will continue with standard of care treatment.

664

665 6.4.4 Sample Size Estimation

666

667 30-50 status post shoulder stabilization surgery meeting inclusion and exclusion criteria will
668 be recruited for this study. A priori sample size calculation using G Power 3.1.2 was
669 performed and it was determined the required sample size would be 34 subjects. This sample
670 size provides 80% power to detect an effect size of 1.0 at the eight week follow-up with an
671 alpha level of .05. To account for a potential 10-15% of subjects lost to follow-up, 38
672 subjects is the goal for recruitment.¹⁴ Multiple prior studies on TDN of upper quarter
673 musculoskeletal disorders have reported very large changes (effect sizes > 1.5) in range of
674 motion after TDN.^{20,27}

675

676 6.5 Reporting Adverse Events

677

678 6.5.1 Expected Adverse Events from Research Risks and Reporting Describe the
679 expected adverse events from research risks using the following categories (the event
680 rates may be derived from your clinical experience or literature).

681

- Rare but serious (Event Rate < 1%):

Collapsing Lung

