90 stabilization surgery. Measurements of the aforementioned dependent variables will be taken
91 at time intervals of four weeks, eight weeks, 12 weeks, and six months post-operatively. It is
92 hypothesized that the inclusion of dry needling will result in an increase in range of motion,
93 increase in functional movement, and decrease in pain at an accelerated rate when compared
94 to rehabilitation alone. Findings will potentially lead to insights as to the benefit of applying
95 this intervention to additional body regions.
96

97 **2.2 Research Design**

98 The research design will be a single-blinded randomized controlled trial.
99

100 **2.3 Methodology /Technical Approach**

101 30-50 subjects at least four weeks after shoulder stabilization surgery will be
102 randomized into two groups (one experimental group and one control group). Subjects in the
103 experimental group will receive Trigger Point Dry Needling (TDN) intervention with
104 standard rehabilitation protocol (Appendix A) while subjects in the control group will receive
105 the same standard rehabilitation protocol without TDN. The experimental group will receive
106 trigger point dry needling one time per week for four to six weeks in addition to the standard
107 rehabilitation protocol. The control group will receive only the standard rehabilitation
108 protocol. Baseline measurements will be taken at approximately four weeks post operatively,
109 and subsequent measurements will be recorded at eight weeks, 12 weeks, and six months.

110 All patients who have undergone a shoulder stabilization procedure will be invited to
111 participate. Description of the study and informed consent will take place prior to
112 randomization. Concealed randomization will take place 0-7 days post-operatively.

113 At 4 weeks post-operatively, the following assessment tests will be undertaken:
114 supine shoulder flexion, supine shoulder external rotation, supine shoulder internal rotation,
115 functional movement testing, functional outcome measures, and the numeric pain rating
116 scale.^{1,2,3} Those subjects in the 'experimental group' will receive manual palpation of all
117 upper quarter muscles, including the cervical and thoracic spine region, to detect the presence
118 of myofascial trigger points (TPs). Dry needling will be performed to all detected TPs by a
119 provider trained and experienced in TDN.

120 In addition to the TDN intervention, the experimental group subjects will undergo a

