359 human participants will yield the most applicable and generalizable results.

360 Dry needling has been shown to have minimal risk to subjects with reported
361 frequency of significant adverse effects occurring in less than 1% of sessions.^{17, 43} The
362 most common adverse effects are post needling soreness, hematoma at needling site and
363 pain.^{17, 43, 44} The application of dry needling to the protocol and conducting on human
364 subjects is reasonable and risks to the subjects are minimal.

366 6. PLAN

368 6.1 New Investigational Drugs/Investigational Devices Exemption Status 369 N/A

371 6.2 Selection of Subjects

373 6.2.1 Type of the Subject Population

375 Participants for this study will be Department of Defense (DOD) healthcare beneficiaries at
376 West Point and Keller Army Community Hospital age 18 years to 40 presenting status post
377 shoulder stabilization repair surgery. In the event that an emancipated, 17 year old cadet
378 meets inclusion criteria for the study, they will also be allowed to participate.

380 6.2.2 Inclusion and Exclusion Criteria

Inclusion	Exclusion
Age 18-40 DOD beneficiaries (17 if Cadet)	Self-Reported Pregnancy
Status post shoulder stabilization repair surgery	History of blood borne pathogens/infectious disease/active infection/metal allergy
	Bleeding disorders or currently taking anti- coagulant medications
	Participants who are not fluent in English

382
383
384 The PI is not fluent in languages other than English and is unable to have study materials
385 translated and certified in other languages. For this reason, we are not able to
386 accommodate participants who speak languages other than English.

388 6.2.3 Recruitment

389 a. Subject selection must be equitable.

391 There is a high feasibility of recruiting 30-50 subjects for this study within an
392 eight month timeframe. This is based on the number of shoulder stabilization
393 procedures performed at Keller Army Hospital that average 8 per month. To our
394 knowledge, the other studies that involve this population do not include subjects
395 status post shoulder stabilization repair and are not receiving TDN. There is a low
396 likelihood that subjects able to participate in our study will already be participating in
397 another injury study of this nature.

398 Given the inclusion and exclusion criteria, any subject that presents status post
399 shoulder stabilization repair has the possibility of being recruited into the study. We

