400 have selected the age ranges based on the general accessible population. Selection of
401 age ranges 18-40 (17 if cadet) are to include the typical ages of Cadets and other
402 personnel at West Point. There is no exclusion criteria that would specifically
403 exclude any gender, race or ethnicity. The study population will reflect that of the
404 corps with regards to race, ethnicity, and gender.

405

406 a. **Describe from when, where and how the study subjects will be recruited.**

407 Subjects will be recruited from the population of patients that present to the ~~Arn~~ in
408 and Keller Physical Therapy clinics status post shoulder stabilization repair surgery.
409 When potential subjects present to physical therapy, they will be screened by the PI in
410 accordance with the standard of care following shoulder stabilization surgery. Upon
411 meeting the inclusion criteria, all subjects will be oriented to the need and purpose of
412 the research, invited to participate, and if willing, provided with informed consent.

413 After obtaining consent, the subject will be randomly assigned to treatment groups
414 using a random number generator. All subjects will be evaluated by the PI or
415 designated provider using a normal physical therapy evaluation as part of the standard
416 of care that patients would receive regardless of study participation or not. Subjects
417 that decline to participate in the study or do not meet inclusion criteria will be
418 provided care for their injury as would normally occur.

419

420 b. **Compensation for participation.**

421 Participants will receive no compensation.

422

423 6.2.4 Consent Process

424

425 a. Participants will be consented by the PI or other study staff designated by the PI. The PI
426 will provide copies of the IRB approved consent form to each participant and provide a
427 verbal outline of the study as described in the consent form. Participants will then be
428 encouraged to read the consent form and will be allowed up to 24 hours if requested
429 before signing to appropriately weigh the risks and benefits to them. Throughout the
430 consent process, participants will be instructed that participation is voluntary and that
431 their decision to participate or withdraw will have no bearing on their career, educational
432 status, or overall medical care.

433

434 b. The consent form will be written in layman's terms at an eighth grade reading level.

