435 Participants will be given up to 24 hours if requested to read the consent form and ask
436 questions prior to signing the consent form. In the event that participants do not wish to
437 take the whole 24 hours, they may consent immediately. In this case, the PI will review
438 the consent form prior to participant signature.
439

440 **6.3 Study Design and Methodology**

441 **6.3.1 Study Design**

442 This study will be a single-blinded, randomized controlled trial with repeated
443 measures design. Outcome assessors will remain blinded from group assignment and perform
444 measurements related to the study protocol at 4 weeks post-intervention, 8 weeks, 12 weeks,
445 and 6 months. The PI or an AI will consent each subject and open a sealed envelope to reveal
446 the subjects intervention group. Concealed allocation to treatment group will be performed
447 by an individual not involved in subject recruitment or treatment, using a computer generated
448 randomized table of numbers created for each participating site prior to the beginning of the
449 study. The group assignment will be recorded on an index card. This card will be folded in
450 half such that the label with the patient's group assignment is on the inside of the fold. The
451 folded index card will be placed inside the envelope, and the envelope will be sealed. The PI
452 or an AI, trained in TDN, will perform dry needling interventions and will not participate in
453 outcome measurements related to the study protocol. Blinded outcome assessors will repeat
454 all study related measurements at a follow up at 8 weeks, 12 weeks, and 6 months. Group
455 assignment will not be combined with subject data until all measurements have been
456 completed at the final six month follow up. Over the course of rehabilitation, subjects will
457 engage in a standard protocol as described previously. This will include frequent re-
458 assessment, measurement, and progression of rehabilitation that is the standard of care for
459 this procedure.
460

461 **6.3.2 Study Methodology/Procedures**

462 **GROUPS**

463 **Group assignment will be recorded with individual subject identifier and secured in a**
464 **separate folder until completion of all data collection through the final follow up.**
465

466 -Experimental Group: Upper Quarter TDN with shoulder stabilization protocol
467 -Control Group: Shoulder stabilization protocol alone

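### Section 2.3 gives two incompatible randomization times; the other sections point to about day 7, so the week-4 outcome baseline follows allocation, with no stated reason

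*Combined protocol and SAP*

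**What the plan says.** Section 2.3 makes three statements about timing:

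- "30-50 subjects at least four weeks after shoulder stabilization surgery will be" is followed directly by "randomized into two groups (one experimental group and one control group", which puts randomization at week 4 or later.
- "Baseline measurements will be taken at approximately four weeks post operatively" makes week 4 the outcome baseline.
- "Concealed randomization will take place 0-7 days post-operatively" puts randomization in the first week.

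Other sections describe how allocation works:

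- Section 6.2.3: "After obtaining consent, the subject will be randomly assigned to treatment groups".
- Section 6.3.1: "The PI or an AI will consent each subject and open a sealed envelope to reveal" the assigned group. The list behind the envelopes is a "randomized table of numbers created for each participating site prior to the beginning of the" study.
- Section 6.3.2 has a visit headed post-operative day ~7. Consent, numeric identifier and group assignment all occur there. Both groups then follow the post-operative protocol until the 4-week visit, and needling treatments 1-4 fall in weeks 4-8.
- The section 6.3.5 table marks Randomization under Baseline, a column before the 4-week column. Range of motion is first marked at 4 weeks.

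Sections 6.3.4 and 6.4 define the 2x4 repeated measures ANOVA with week 4 as the first of its four time levels.

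**The concern.** A baseline is most useful when nobody's knowledge of the arm can have touched it. Here planned care does not differ until after the week-4 measurements, so revealing the arm in the first week brings no benefit that the protocol states. It does let the PI or an AI know the arm during early rehabilitation. The scientific review letter says that the same therapists administer both the needling and the standard rehabilitation, and section 6.3.2 says that routine reassessment is not blinded.

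Three things are at stake:

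- Whether the week-4 values are a true pre-allocation baseline.
- Whether early rehabilitation is delivered without knowledge of the arm.
- Whether someone who leaves between day 7 and week 4 counts as a randomized loss. Such a subject would have no range-of-motion or function value at any level of the ANOVA.

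**Working it through.** **1. Which time do the sections support?**

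| Section | Gives a day? | Gives an order? |
|---|---|---|
| 2.3, first statement | week 4 or later | no |
| 2.3, second statement | day 0-7 | after consent |
| 6.2.3 | no | assignment after consent |
| 6.3.1 | no | envelope opening tied to consent |
| 6.3.2 | day ~7 | consent and assignment at the same visit |
| 6.3.5 | Baseline column | before the 4-week column |

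No single operational section settles the matter. Section 6.3.1 alone gives no day. Together, 6.2.3, 6.3.1, 6.3.2 and 6.3.5 agree with the day 0-7 sentence and not with the four-week sentence.

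**2. Gap between allocation and baseline.** Week 4 is day 28. 28 - 7 = 21 days and 28 - 0 = 28 days, so the gap is 21 to 28 days.

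**3. What is exposed at week 4?**

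- Range of motion and function: sections 6.3.1 and 6.3.2 require blinded assessors, so these are largely protected. One loose end is that section 6.3.2 has the AI record the data, while the same section lets an AI know the assignment.
- NPRS (one of three primary outcomes), PSFS and SPADI: exposed only if subjects know their arm. Section 6.3.2 says that assignment is provided at the day-7 visit, without saying to whom, and also that only the PI or AI knows it.
- Earlier values: the 6.3.5 table marks NPRS, PSFS and SPADI at Baseline, and 6.3.4 puts NPRS on the baseline questionnaire. Some self-reports may therefore exist from that visit, but whether before or after the envelope is opened is not stated. Range of motion and function have no earlier value.

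**4. Attrition.** Inputs from section 6.4.4: effect size 1.0, alpha .05, 80% power, 34 required, 10-15% loss, goal 38. Sidedness and test are not stated; a two-sided two-sample t-test with equal arms is assumed.

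- Reproduction: 16.71 per arm, so 17 per arm and 34 in total, with power 80.7%. 34/0.90 = 37.8, so 38; 34/0.85 = 40.0.
- Margin: 38 - 34 = 4 subjects, and 4/38 = 10.5%.
- Power by number remaining: 80.7% with 34, 78.1% with 32, 76.7% with 31.
- Loss of 10% or 15% from 38: 38 × 0.90 = 34.2 and 38 × 0.85 = 32.3, taken as 34 and 32.
- The same after 2 early losses (an assumption; the documents give no early-loss rate): 36 × 0.90 = 32.4 and 36 × 0.85 = 30.6, taken as 32 and 31.
- Difference: 80.7 - 78.1 = 2.6 points at 10% loss, and 78.1 - 76.7 = 1.4 points at 15%.

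**The case against.** Randomizing at consent and giving both arms the same care until treatment starts is a legitimate design. The operational sections describe it coherently, and only one sentence in the abstract departs from it. On that view, correcting the sentence and saying whether subjects are told their arm would suffice. Much of this stands. Early opening does not invalidate the randomized comparison, and a direct between-group comparison at week 8 does not use week 4.

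Three stronger readings are tempting, and the documents do not support them:

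- **Early opening inflates the false-positive rate of the group-by-time test.** Suppose self-reports differ between arms by a purely assumed 0.1-0.3 SD (17 per arm, compound symmetry, correlation .5-.7). If the shift is present at week 4 and gone by week 8, the rate is 5.7-17.9% with early opening and 5.0% with late opening. If half persists, it is 5.2-7.8% under both. If it fully persists, early opening gives 5.0% and late opening 5.7-17.9%. Arm differences of (d, 0, 0, 0) and (0, d, d, d) produce the same interaction. This takes the later shift to be the same under both designs, since later self-reports are unblinded either way. Nothing in the documents says which pattern is likelier, so the error rate is no argument for moving the envelope.
- **The week-4 self-reports are biased.** That needs subjects to know their arm, which section 6.3.2 does not establish.
- **Early losses leave the trial underpowered.** The 10-15% allowance is not restricted to losses after week 4 and may already include them. The protocol also allows 30-50 subjects, so 38 is a goal rather than a ceiling.

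What the objection does not remove: section 2.3 contradicts itself, the only range-of-motion and function baseline follows allocation, and no reason for that order is given.

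**Conclusion.** The contradiction in section 2.3 is established and needs reconciling. Allocation at about day 7 is the better-supported reading. It rests on several sections taken together, so confidence in it is medium. Under it, the arm is revealed 21-28 days before planned care differs, and the first ANOVA level is post-allocation.

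The practical effect is limited. Its direction and size for self-reports and early rehabilitation are unknown. The power effect is about 1-3 points, and only if two early losses come on top of the stated allowance. Opening the envelope after the week-4 measurements is a worthwhile, inexpensive improvement rather than the repair of an invalid design. It makes the baseline truly pre-allocation, hides the arm during early rehabilitation, and turns withdrawals before week 4 into non-randomized ones.

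**What to change.** **Preferred.**

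- Keep consent, numeric identifier and demographics at day 0-7. Leave the envelope sealed until the week-4 measurements are recorded, and open it before the first needling session.
- Move Randomization in the 6.3.5 table to after the 4-week measurements. Make both statements in 2.3, and 6.2.3, 6.3.1 and 6.3.2, agree.
- Define the goal of 38 as randomized subjects. Let identifiers run past 38 so that a withdrawal before randomization can be replaced. A range of 1-50, using the protocol's own upper figure, covers early loss up to 1 - 38/50 = 24%.

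**Cost.** The list, envelopes and visits are unchanged. Visits are dated from surgery, so no follow-up is lengthened. The downsides are:

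- Needling can be booked only after the week-4 visit.
- The randomized group is limited to subjects still enrolled at week 4.
- Self-reports after week 4 stay unblinded.
- More consents may be needed. At an assumed early loss of 5%, 10% or 15%: 38/0.95 = 40, 38/0.90 = 42.2 (so 43), 38/0.85 = 44.7 (so 45). Section 6.2.3 cites "procedures performed at Keller Army Hospital that average 8 per month", and 8 × 8 months = 64. The shares are 62.5%, 67.2% and 70.3%, against 38/64 = 59.4%, if all 64 are eligible. The scientific review letter calls the fellowship time limit the study's biggest challenge, so this matters.

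**If early opening is kept.** Reconcile section 2.3, give the reason, state whether subjects learn their arm before week 4, and require the Baseline self-reports to be completed before the envelope is opened.

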324 electrical activity within a TP.^{36, 37, 38} Mechanically, TDN could disrupt the integrity of
325 dysfunctional motor endplates related to shortened muscle fibers.²⁵ TDN may evoke a
326 neurophysiological reset²⁵ as well as mechanically disrupt taut bands of muscle tissue found
327 in areas of muscle dysfunction, allowing for normalized range of motion of the targeted
328 muscle fibers favorably affecting pain and tension in the affected regions.^{35, 39} These effects
329 appear to be most effective when a local twitch response is elicited.³⁸
330
331
332

This picture is an example of
the needles that would be used
for the intervention. Please note
the actual needle placement and
size will differ between
participants.

333
334
335
336
337

5.2 Scientific Justification.

338 This study will address the potential benefits of TDN and rehabilitation against
339 rehabilitation alone to improve range of motion of the shoulder, assess improvements in
340 functional movement, and patient reported changes in pain in a population of post-operative
341 shoulder stabilization repair patients. Findings may lead to insights as to the benefit of
342 applying this intervention to additional regions of the body. If there is an increase of ROM
343 and functional movement or decrease in pain, TDN may be used as an adjunct to current
344 methods to ultimately provide better patient outcomes. Finding better and more effective
345 interventions may help rehabilitation providers be more effective at preserving the fighting
346 force and improving combat effectiveness.

347 Military musculoskeletal providers as well as soldiers and athletes are constantly
348 seeking the fastest most effective treatment strategies to improve performance on the
349 battlefield or the playing field. TDN has become a popular intervention with these
350 populations, however, there is a paucity of evidence to explain or support the intended
351 benefit.¹⁶ The results of this study will add to the limited body of research on this topic as
352 well as assist musculoskeletal providers in making evidence based decisions justifying the
353 use of this treatment modality.

354
355 **5.3 Human Use Justification.**

356 This study is designed with human subjects because that is the population of interest,
357 and the surgical procedures for shoulder stabilization are performed on humans.
358 Additionally, the results of this study will be used to further treatment with humans, therefore

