580 administered, if any. As appropriate, include the validity and reliability of the instruments.
581 For subject's confidentiality protection, outline the procedure for coding, recording, storing
582 and protecting the data. Provide a copy of data collection sheets, case report forms, survey
583 forms/questionnaires/instruments, and/or a copy of the author's permission granting the use
584 of the instruments in the *Appendix Section 20*.

585

586 All data will be collected through survey questions and direct researcher measurements.

587

588

589

590

591 Data collected and Time Points

SURVEY DATA	OBJECTIVE MEASUREMENTS
Age -baseline demographic questionnaire	Glenohumeral Internal Rotation - initial data collection, at each follow up
Gender -baseline demographic questionnaire	Glenohumeral External Rotation - initial data collection, at each follow up
Duration of symptoms -baseline demographic questionnaire	Glenohumeral Flexion - initial data collection, at each follow up
Numeric Pain Rating Scale (NPRS) for shoulder pain -baseline demographic questionnaire - initial data collection, at each follow up	Functional Range of Motion Test - initial data collection, at each follow up
	Global Rating of Change (GROC) -at each follow up
	PSFS -initial data collection, at each follow up
	SPADI -initial data collection, at each follow up

592

593 Study Variables

INDEPENDENT VARIABLES	DEPENDENT VARIABLE
Group Assignment (2 Levels) 
 - Experimental - Control 	Shoulder Range of Motion 
 -Internal Rotation (degrees) - External Rotation (degrees) - Flexion (degrees) -Functional Movement Test
Time (4 Levels) 
 - Week Four - Week Eight - Week 12 - Month Six 	Shoulder pain (NPRS) 
 -with internal rotation - with external rotation - with flexion - with functional movement test
	GROC
	PSFS
	SPADI

594

595

596 Data Collection/Confidentiality

597 Subjects will sign the consent forms but no identifiable information will be on data collection
 598 forms. Each of the subjects will be randomly assigned a subject identification number from
 599 1-38 upon entrance into the study and subsequently given consent forms and survey/data
 600 collection forms with the corresponding number. Each number assigned will only be used
 601 once.

602 All subject information and data collection forms will be kept behind double locks: in

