 603 a locked filing cabinet, behind a locked door. Signed consent forms, group assignment, and
 604 data collection forms will all be kept in separate folders and filing cabinet drawers. All
 605 electronic study databases will be secured on password protected computers and stored on a
 606 server with restricted access requiring CAC authentication. Subject data will only be
 607 identified by each subject's identification code.

608

609

610 **6.3.5 Study Time Line**

611

612 **Demographic/ Data Collection and Intervention Timeline**

613

614

	Baseline	4 weeks	Tx 1-4; Experimental Group Only	8 weeks	12 weeks	6 months
Informed Consent, Discuss Plan, etc	x					
Screening, Demographics	x					
Randomization	x					

History and Physical		x		x	x	x
TDN to Experimental group			x			
HEP Instruction	x	x		x	x	x
ROM Measurement		x		x	x	x
GROC	x	x		x	x	x
PSFS	x	x		x	x	x
NPRS	x	x		x	x	x
SPADI	x	x		x	x	x

615

616

617 **6.4 Statistical Consideration**

618 Descriptive statistics will be provided. Data analysis will be performed with statistical
 619 analysis software R version 3.1.2. A 2x4 repeated measures ANOVA with Sidak's post hoc
 620 testing will be used with time as the within-subjects factor and group (control or TDN) as the
 621 between-subjects factor.

622

623 **6.4.1 The primary endpoints (i.e., primary outcome variables) and the secondary**
 624 **endpoints, if any.** Clearly define primary and secondary outcome variables of the research
 625 study.

626 Outcome variables for this study are as follows:

627 **Primary Outcomes:**

1. **Passive Range of Motion:** Changes in range of motion of the shoulder, as measured by glenohumeral range of motion during passive shoulder flexion, external rotation, and internal rotation, and are necessary outcome variables to determine the effectiveness of dry needling of shoulder TPs in a post-operative population.⁸
2. **Shoulder Functional Movement Test:** To assess overall change in movement mechanics of the shoulder. Functional Movement patterns are needed to perform complex tasks such as pull-ups and pushups.³
3. **Numeric Pain Rating Scale (NPRS):** Severity of pain in the shoulder with functional activities at each visit will be assessed using a scale from 0-10. The subject will report their level of pain with the instruction that "0 is no pain, 10 is the worst pain imaginable".^{6,18}

640 **Secondary Outcomes:**

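### Three unranked primary outcomes (five variables as worded) have no success rule, so the stated 5% alpha and 80% power hold only for one comparison that the plan does not name

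*Combined protocol and SAP*

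**What the plan says.** **Primary outcomes.** Section 6.4.1 names three:

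- passive range of motion, "as measured by glenohumeral range of motion during passive shoulder flexion, external rotation, and internal rotation, and are necessary outcome variables" (three variables, with no composite and no lead direction);
- the functional movement test (worded as one variable);
- the NPRS (worded as one variable).

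The list is numbered, but nothing says that the numbers are a testing order.

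**Analysis.** Section 6.4.2 specifies "A 2x4 repeated measures ANOVA with Sidak's post hoc" testing, with time within subjects and group as the "between-subjects factor. Alpha will be = .05". Sidak is attached to this ANOVA and is not extended across outcome variables. The plan does not say whether the interaction must be significant first, or which contrasts Sidak covers.

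**Sample size.** Section 6.4.4 requires 34 subjects for "80% power to detect an effect size of 1.0 at the eight week follow-up", and names no variable. It continues: "To account for a potential 10-15% of subjects lost to follow-up, 38" is the recruitment goal.

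**What would count as success.** The hypothesis in Section 2.1 joins range of motion with "increase in functional movement, and decrease in pain at an accelerated rate when compared". Section 5.2, on adoption, reads "and functional movement or decrease in pain, TDN may be used as an adjunct to current". The first suggests that all domains must improve, the second that one route may be enough.

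**Pain.** The NPRS is rest and activity pain in Section 2.3, pain during functional activities in Section 6.4.1, and pain at each measurement in Section 6.3.2. The Study Variables table in Section 6.3.4 lists four NPRS scores.

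**The concern.** With several primary variables and one undivided alpha, the error rate and the power of the trial depend on the rule that turns the tests into a conclusion. The plan gives no such rule.

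If any single significant primary supports dry needling, the chance of a false claim is above that of one test. If all primaries must be significant, the false-positive rate is controlled but power falls well below 80%.

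The choice of rule, of range-of-motion direction and of pain variable could be made after the results are seen. A reader could not then tell a confirmed effect from the best of several tests.

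**Working it through.** **Inputs from the documents:** alpha .05, d = 1.0, 34 evaluable subjects, week 8 (6.4.4); five primary variables as worded (6.4.1).

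**Assumptions:** 1:1 allocation and two-sided tests, neither of which is stated; a common correlation between outcomes of 0 to 0.9, because the documents give none.

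**1. The plan's own figure.** For a two-sample t test with n per arm, the noncentrality is d x sqrt(n/2) on 2n - 2 degrees of freedom.

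- n = 17: sqrt(8.5) = 2.92, 32 df, power 80.7%.
- n = 16: sqrt(8) = 2.83, 30 df, power 78.1%.

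So 2 x 17 = 34 is reproduced as one two-sided comparison. A one-sided test would reach 80% at 14 per arm (28 in total; 82.4%), so it does not fit. With 38 recruited, 38 x 0.90 = 34.2 and 38 x 0.85 = 32.3. The goal therefore keeps 34 evaluable at 10% loss, and 32 (78.1% power) at 15%.

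**2. If any one primary counts, one week 8 test each.** Under independence the two-sided rate is 1 - 0.95^k:

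- k = 3: 1 - 0.8574 = 14.3%, or 2.9 times 5%.
- k = 5: 1 - 0.7738 = 22.6%, or 4.5 times 5%.

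With a common correlation (simulated):

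| Correlation | 3 tests | 5 tests |
|---|---|---|
| 0 | 14% | 23% |
| 0.5 | 12.5% | 18% |
| 0.7 | 11% | 15% |
| 0.9 | 8% | 10% |

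False results favouring needling are half of these or slightly more. For five tests they are 12.1 / 9.3 / 7.5% at correlations 0 / 0.5 / 0.7, against 2.5% for one test.

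**3. Other readings of the ANOVA and Sidak steps.** These come from 40,000 simulated null trials with 17 per arm, four visits, within-subject correlation 0.5 (assumed) and outcome correlations 0 / 0.5 / 0.7.

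| Reading | One variable | Five variables |
|---|---|---|
| Sidak over three follow-up contrasts, no gate; favouring needling | 2.3% | 10.9 / 8.7 / 7.3% |
| Interaction significant first, then those contrasts; favouring needling | 0.5% | 2.4 / 2.1 / 1.8% |
| Interaction first, then Sidak on changes from week 4; favouring needling | 1.4% | 6.7 / 5.5 / 4.6% |
| Interaction alone counts; either direction | 5.0% | 22.6 / 18.6 / 15.4% |

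**4. If all must succeed, d = 1.0 on each, week 8.**

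- Three variables: 0.807^3 = 53% if independent, about 67% at correlation 0.7.
- Five variables: 0.807^5 = 34% if independent, about 60% at correlation 0.7.

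**5. Holm on three variables at 17 per arm, d = 1.0 each, correlation 0 / 0.5 / 0.7.**

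- At least one success: 95.8 / 87.3 / 82.3%.
- Average per outcome: 75.2 / 73.6 / 72.6%.
- All three: 50.4 / 59.5 / 63.4%.

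**The case against.** The strongest reply is that the size of the inflation is not fixed by the documents. These are measures of one shoulder in the same patients, so positive correlation is likely. At 0.9, five tests give about twice 5%, and three tests about 1.7 times. If post hoc means that Sidak is used only after a significant interaction, the rate favouring needling for five variables is about 2%, no higher than the nominal one-sided 2.5%. All of this stands. A reader might infer a fixed multiple of 3 to 5, but that holds only for five variables at correlations of 0 to 0.7. It does not remove the point, because the plan does not state the gate and the correlations are unknown.

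A reader might also count eight primaries (four NPRS scores) or ten (the three functional tests in Section 2.3 analysed separately). Section 6.4.1 words both items singly, and the data sheets are assigned to an appendix that is not in the public text. Five is therefore the supportable count.

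It could also be said that the hypothesis in Section 2.1 already requires every domain to succeed. The adoption sentence in Section 5.2 points the other way, and neither is written as a decision rule.

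Finally, a reader might take external rotation as the obvious single primary, because the title of reference 11 reports that it is commonly restricted after surgery for anterior instability. That is too little. Section 6.4.1 treats all three directions as necessary, and Section 6.2.2 admits any stabilization repair.

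**Conclusion.** The point holds. The plan has three unranked primary outcomes, five variables as worded, one undivided alpha of .05 and no success rule. Sidak within the ANOVA does not cover testing across variables. Alpha .05 and 80% power hold together only for one two-sided week 8 comparison on a variable that is not named.

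The size is conditional:

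- **Any one counts, one week 8 test each:** up to 14% (three tests) or 23% (five) if independent; for five, about 15-18% at correlations 0.7-0.5 and about 10% at 0.9.
- **Significant interaction required first:** lower in absolute terms, about 2% favouring needling on one reading and 5-7% on another.
- **All must succeed at d = 1.0:** about 53-67% power for three variables and 34-60% for five, at correlations 0 to 0.7.

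These figures assume 1:1 allocation, 17 per arm and equal correlations. The documents do not support the stronger statement that the trial's false-positive rate is known to be several times 5%. They do support saying that it cannot be determined from the plan.

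**What to change.** Amend the plan by addendum, as Section 14 requires, before any outcome data are examined by group. The merging of assignment with data (Section 6.3.1) is not by itself a safe cut-off. Section 6.3.2 lets the PI or AI know the assignment and leaves routine rehabilitation measurements unblinded.

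Choose one of two routes:

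1. **One primary variable at week 8.** The investigators choose and justify it, and name only one. All other variables become secondary. N = 34 and the goal of 38 stay. The cost is fewer routes to a positive claim, and if pain becomes secondary, Objective 2 in Section 3 is no longer tested as a primary question.
2. **Three domains, matching Objectives 1 and 2.** Prespecify one variable per domain, including one NPRS definition used throughout, and test them by Holm at week 8. State the success rule and restate power at 34 evaluable: about 82-96% for at least one, 73-75% on average per outcome, 50-63% for all three. The cost is a less favourable stated power. About 80% average power would need 38-40 evaluable, or 43 (38/0.90) to 48 (40/0.85) recruited. That lies within the 30-50 range but above the goal of 38 and the identifiers "1-38 upon entrance into the study and subsequently given consent forms and survey/data" forms.

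Under either route, state how the ANOVA and Sidak steps relate to the week 8 test, and align the Section 5.2 adoption sentence with the chosen rule. No new measurements are needed. The inconsistencies on the needling schedule and on assessor blinding are separate matters, where the sections should be reconciled on their own.
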